9.7.1.8.3 LABORATORY VALUES

Clinical laboratory values will be evaluated for each laboratory parameter by subject. Abnormal laboratory values will be identified as those outside (above or below) the normal range. Reference (normal) ranges for laboratory parameters will be included in the CSR for this study. Descriptive summary statistics (eg, mean, SD, median, minimum, maximum for continuous variables, and number and percentage for categorical variables) for the laboratory parameters and changes from Study Baseline will be evaluated by treatment group and visit. This will also be repeated for the 12-month LEM exposure (On-Treatment Safety Analysis Set), summarized by treatment group and duration of exposure. (revised per Amendment 06)

Laboratory test results will be assigned a low, normal, high (LNH) classification according to whether the value was below (L), within (N), or above (H) the laboratory parameter's reference range. Within-treatment comparisons will be based on 3 by 3 tables (shift tables) that, for a particular laboratory test, compare the Study Baseline LNH classification to the LNH classification at Month 6 by treatment group. This will also be repeated for the 12-month LEM exposure (On-Treatment Safety Analysis Set), summarized by treatment group and duration of exposure. (revised per Amendment 06)

Clinical laboratory results post-Study Baseline will be evaluated for markedly abnormal values. A laboratory test will be considered markedly abnormal if the result worsens to meet Eisai grading criteria for laboratory values limit of Grade 2 or higher. If the Grade 2 limit is missing, the Grade 1 limit will be considered. [Appendix 1](#) presents the Eisai grading criteria for laboratory values that were used to identify subjects with markedly abnormal laboratory values. For the incidence of markedly abnormal laboratory values, each subject may be counted once in the laboratory parameter value high and in the laboratory parameter low categories as applicable.

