9.7.1.8.5 ELECTROCARDIOGRAMS

Descriptive statistics for ECG parameters and changes from Study Baseline (Safety Analysis Set) will be presented by treatment group and visit. This will also be repeated for the 12-month LEM exposure (On-Treatment Safety Analysis Set), summarized by treatment group and duration of exposure. (revised per Amendment 06)

Shift tables will present changes from Study Baseline in ECG interpretation (categorized as normal and abnormal) by time point. (revised per Amendment 03)

For each subject, the maximum observed QTcF, the corrected QT interval calculated using Bazett's formula (QTcB), and the maximum prolongation from Study Baseline in QTcF will be compiled. Categorical analyses of subjects (number and percent) with maximum observed QTcF values >450 ms, >480 ms, and >500 ms and maximum prolongations (from Study Baseline) in QTcF >30 ms and >60 ms will be presented by treatment group and by time point. Categorical analyses of subjects (number and percent) with maximum observed PR values >220 ms, and QRS values >120 ms will be presented by treatment group and by time point. This will also be repeated for the 12-month LEM exposure (On-Treatment Safety

Analysis Set), summarized by treatment group and duration of exposure. (revised per Amendment 06)

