3.2.5 Prior and Concomitant Therapy

All investigator terms for medications recorded in the eCRF will be coded to an 11-digit code using the World Health Organization Drug Dictionary (WHO DD; Mar 2017 or latest version). If the Safety Analysis Set and FAS differ, then the prior and concomitant medication summaries will be repeated on the FAS.

Prior medications are defined as medications that stopped before the first dose of study drug, where study drug includes placebo during the Run-In Period.

Concomitant medications are defined as medications that (1) started before the first dose of study drug (including placebo Run-In Period) and are continuing at the time of the first dose of study drug, or (2) started on or after the date of the first dose of study drug (including the placebo Run-In Period) to the last dose day plus 14 days.

For the Run-In Period, a concomitant medication is defined as a medication that started on or before the 1st dose of study medication of the Run-In Period and continued during the Run-In Period, or started during the Run-In Period. For Period 1, a concomitant medication is defined as a medication that started on or before the 1st dose of study medication of Period 1 and continued during Period 1, or started during Period 1. For Period 2, a concomitant medication is defined as a medication that started on or before the 1st dose of study medication in Period 2 and continued during Period 2, or started during Period 2.

The number (percentage) of subjects who take prior and concomitant medications will be summarized on the Safety Analysis Set by treatment group, Anatomical Therapeutic Chemical class (ATC) and World Health Organization Drug Dictionary-preferred term (PT). If the Safety Analysis Set and FAS differ, then the prior and concomitant medication summaries will be repeated on the FAS.

If the subject has taken the same concomitant medication (as coded to preferred WHO-drug term) more than once, the subject will be counted only once in the tabulation.

Separate summaries of concomitant medications will be provided for Run-in Period (using Safety Analysis Set), Period 1 (using Safety Analysis Set), Period 2 (using On-Treatment Safety Analysis Set) and Period 1 plus Period 2 (using On-Treatment Safety Analysis Set).

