3.6.1 Treatment Definitions

For visit-based Safety data (ie, laboratory values, vital signs, ECGs, etc) data will be summarized by treatment (LEM5, LEM10) and duration of exposure to treatment (3, 6, 9 and 12 months). Treatment groups are LEM5 and LEM10, and include both (a) LEM Period 1 subjects on the On-Treatment Safety Analysis Set using the change from Study Baseline and (b) LEM Period 2 subjects previously receiving PBO on the On-Treatment Safety Analysis Set using the change from Period 2 Baseline. Summaries of exposure, AEs, TEMAV, clinically abnormal vital sign and ECG values will be summarized for:

- Period 1 data, where treatment groups are PBO, LEM5 and LEM10 in the Safety Analysis Set (ie, subjects who received at least 1 dose of study drug in Treatment Period 1)

- 12-month LEM exposure, where treatment groups are LEM5 and LEM10 in the On-Treatment Safety Analysis Set (ie., subjects who received at least 1 dose of lemborexant), where data will be summarized by exposure to treatment (3, 6, 9 and 12 months)

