3.6.4 Laboratory Values

Laboratory results will be summarized using Système International (SI) units, as appropriate. With the exception of urinalysis, all quantitative parameters listed in [protocol Section 9.5.1.5.3 Laboratory Measurements](#), the actual value and the change from Study Baseline will be summarized at each scheduled visit using descriptive statistics by treatment group. The change from Study Baseline/Treatment Period 2 Baseline (as appropriate) will also be repeated for the 12-month LEM exposure (On-Treatment Safety Analysis Set), summarized by treatment group and duration of exposure.

For urinalysis, the actual and the change from baseline of pH and specific gravity will be summarized at each visit by treatment group. Analysis of changes from baseline will be based on the number of subjects with both nonmissing baseline and relevant postbaseline results.

Laboratory test results will be assigned a low, normal, high (LNH) classification according to whether the value was below (L), within (N), or above (H) the laboratory parameter's reference range. Shifts from Study Baseline (LNH) to each scheduled visit will be provided by treatment group for each laboratory parameter based on Safety Analysis Set. The shift tables will also be repeated for the 12-month LEM exposure (On-Treatment Safety Analysis Set), summarized by treatment group and duration of exposure.

The Sponsor's Grading for Laboratory Values ([Appendix 1](#)) presents the Eisai criteria that will be used to identify subjects with treatment-emergent markedly abnormal laboratory values (TEMAV). Except for phosphate, a TEMAV is determined if a postbaseline grade increases from baseline and the postbaseline grade is greater than or equal to a grade of 2. For phosphate, a TEMAV was defined as a postbaseline value with an increase from baseline to a grade of 3 or higher.

The number (percentage) of subjects with TEMAVs will be summarized by treatment group using the Safety Analysis Set. The number (percentage) of subjects with TEMAVs will be produced separately for the Period 1, up to 12-months treatment, up to 6-months treatment and On-Treatment. When displaying the incidence of TEMAVs, each subject will be counted

once in the laboratory parameter high and in the laboratory parameter low categories, as applicable.

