3.6.6 Electrocardiograms

Descriptive statistics for ECG parameters and changes from Study Baseline (Safety Analysis Set) will be presented by treatment group. This will also be repeated for the 12-month LEM exposure (On-Treatment Safety Analysis Set), summarized by treatment group and duration of exposure. Shift tables will present changes from Study Baseline in ECG interpretation (categorized as normal; abnormal, not clinically significant; and abnormal, clinically significant) by time point.

In addition, maximum postbaseline measurement will also be tabulated separately for the Period 1 and 12-month LEM exposure by treatment group as follows:

- Number and percentage of subjects with QTcF of >450 msec, and >500 msec during the treatment
- Number and percentage of subjects with a QTcF increment of >30 msec, and >60 msec from the baseline visit.
- Number and percentage of subjects with PR of >220 msec
- Number and percentage of subjects with QRS of >120 msec

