6.2 SAFETY DATA HANDLING

6.2.1 Baseline Safety

The baseline value for all safety endpoints will be the last non-missing measurement occurring prior to the first dose of the study medication.

For visit-based safety summaries there may be two different baseline value as followed:

- Study Baseline: defined as the last non-missing measurement occurring prior to the first dose of the study medication in Period 1.
- Treatment Period 2 Baseline: defined as the last non-missing measurement occurring prior to the first dose of the study medication in Period 2.

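### For subjects switched from placebo, the plan gives conflicting baselines for markedly abnormal laboratory values and QTcF increments in the 12-month lemborexant exposure tables

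*SAP*

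**What the plan says.** SAP 6.2.1 opens with a general rule: "The baseline value for all safety endpoints will be the last non-missing measurement occurring prior to the first dose of the study medication". It continues: "For visit-based safety summaries there may be two different baseline value as followed". The two are a Study Baseline, tied to the first Period 1 dose, and a Treatment Period 2 Baseline, tied to the first Period 2 dose.

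SAP 3.6.1 and protocol 9.7.1.8 set out the 12-month LEM exposure summaries. Both count laboratory values and ECGs as visit-based data. For these data the SAP includes "LEM Period 2 subjects previously receiving PBO on the On-Treatment Safety Analysis Set using the change from Period 2 Baseline". A second sentence in SAP 3.6.1 lists TEMAVs and abnormal vital-sign and ECG values among the outputs to be produced for Period 1 and for 12-month LEM exposure. That sentence names no baseline.

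The output definitions are as follows.

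- **Laboratory (SAP 3.6.4):** "a TEMAV is determined if a postbaseline grade increases from baseline" and reaches at least Grade 2 (Grade 3 for phosphate). The same section takes shift tables from Study Baseline and repeats them for 12-month exposure.
- **QTcF (SAP 3.6.6):** increments above 30 msec and above "60 msec from the baseline visit", tabulated for Period 1 and for 12-month exposure.
- **QTcF (protocol 9.7.1.8.5):** the same cut-offs, applied to "maximum prolongations (from Study Baseline"), and the paragraph is then repeated for 12-month exposure.
- **Vital signs (SAP 3.6.5, Table 8):** the required change is relative to Study Baseline or Period 2 Baseline, whichever is appropriate.

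**The concern.** The 12-month exposure tables pool two kinds of subject under each dose. Those randomized to lemborexant on Day 1 have a Study Baseline immediately before their first lemborexant dose. Those switched from placebo have a Study Baseline about six months before it. For the second group, a table headed by lemborexant exposure but referenced to Study Baseline measures change over placebo time plus lemborexant time.

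Two errors could follow. A laboratory grade or QTcF rise that developed on placebo and was still present after the switch would appear as an event on LEM5 or LEM10. Conversely, a subject who was at Grade 2 at Study Baseline, had improved by Month 6 and returned to Grade 2 on lemborexant would show no grade increase from Study Baseline and would be missed. The same applies to a QTcF that fell on placebo and rose again after the switch. These are the plan's long-term laboratory and QT tables, so the reference point should not depend on which section the programmer reads.

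**Working it through.** **1. The passages side by side, for a former-placebo subject in a 12-month exposure table**

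| Place | Output | Baseline given |
|---|---|---|
| SAP 6.2.1, first sentence | All safety endpoints | One, before first dose |
| SAP 6.2.1, second paragraph | Visit-based summaries | Study or Period 2 |
| SAP 3.6.1, first sentence; protocol 9.7.1.8 | Visit-based data, including laboratory values and ECGs | Period 2 |
| SAP 3.6.4 | Mean laboratory changes | Either, as appropriate |
| SAP 3.6.4 | Shift tables | Study Baseline, then repeated for 12 months |
| SAP 3.6.4 | TEMAVs | Not named |
| SAP 3.6.5, Table 8 | Clinically notable vital signs | Either, as appropriate |
| SAP 3.6.6 | QTcF increments | A baseline visit, not named |
| Protocol 9.7.1.8.5 | QTcF increments | Study Baseline, then repeated for 12 months |

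The SAP names Period 2 Baseline for mean laboratory changes and for Table 8. It does not do so for TEMAVs, shift tables or QTcF increments. A programmer who meets an unqualified baseline could go to the first sentence of 6.2.1 (Study Baseline) or to 3.6.1 (Period 2 Baseline). Each choice can be defended from the text, and they give different tables.

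**2. Share of former-placebo subjects in each dose group**

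Inputs: 300 per arm, 1:1 re-randomization of placebo subjects at Month 6, and a 50% loss by Month 6 as the plan's own high-dropout scenario (protocol 9.7.2, SAP 2). That section also states 420 six-month lemborexant completers. This reproduces as 2 × 150 (original lemborexant arms at Month 6) + 120 (former placebo at Month 12) = 420, so the plan itself counts former-placebo subjects toward lemborexant exposure.

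With placebo loss d by Month 6, the former-placebo number per dose is e = 300(1 − d)/2 and its share is e/(300 + e), taking all 300 originally randomized to that dose as exposed.

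- d = 0: e = 150; 150/450 = 33%
- d = 50%: e = 75; 75/375 = 20%

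**3. Effect on a laboratory rate**

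Let q be the fraction of former-placebo subjects with a qualifying abnormality that arose on placebo and persists after the switch without further worsening. The documents give no value, so q = 1% to 5% is assumed. Study Baseline counts these subjects and Period 2 Baseline does not. The added rate is share × q.

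- Low: 20% × 1% = 0.2 percentage points
- High: 33.3% × 5% = 1.7 percentage points

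This is a gross addition. Worsening missed under Study Baseline acts in the other direction and is not quantified.

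**4. QTcF**

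The ECGs after the switch are at Months 9 and 12. With no drug effect and exchangeable within-subject errors, the larger of those two minus the Month 6 value has the same distribution as the larger of those two minus the Study Baseline value. The expected proportion above 30 msec is therefore the same under either baseline. The baseline choice changes which subjects are flagged, not the expected rate.

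**The case against.** The strongest reply is that the plan, read as a whole, already gives the right answer. SAP 3.6.1 and protocol 9.7.1.8 call laboratory values and ECGs visit-based and give former-placebo subjects Period 2 Baseline, and the exception in 6.2.1 uses the same term. Listing TEMAVs and ECG values in the second sentence of 3.6.1 does not exclude them, because abnormal vital signs are in that same list and Table 8 allows Period 2 Baseline for them. This stands: Period 2 Baseline is an available reading, so misattribution is a risk and not an established result. It does not remove the conflict with protocol 9.7.1.8.5, the shift-table sentence or the general rule in 6.2.1.

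Four stronger readings are tempting, and the documents do not support them.

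- **An abnormality seen only in Period 1 counts under lemborexant.** No passage says that placebo-period values are postbaseline in the 12-month tables. SAP 3.6.1 organizes those tables by lemborexant exposure, and SAP 3.6.6 limits the QTcF threshold counts to the treatment.
- **QTcF flags would roughly double.** That result needs the Month 1, 3 and 6 placebo ECGs to be counted, which no passage directs.
- **The safety baseline is really Screening.** SAP 3.2.5 says "where study drug includes placebo during the Run-In Period", and the first sentence of 6.2.1 omits the word randomized. But 3.2.5 is a medication-classification rule, and 6.2.1 goes on to tie Study Baseline to the first Period 1 dose.
- **The protocol fixes Study Baseline for TEMAVs in the 12-month tables.** Protocol 9.7.1.8.3 does say "Clinical laboratory results post-Study Baseline will be evaluated for markedly abnormal values", but that paragraph has no clause repeating it for 12-month exposure. The protocol evidence is firm only for QTcF.

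The scope is also limited. Safety analyses carry no hypothesis tests, the placebo-controlled Period 1 tables are unaffected, and adverse events have their own Period 2 rules (protocol 9.7.1.8.2, SAP 3.6.3).

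**Conclusion.** The concern holds as an internal conflict. For former-placebo subjects in the 12-month exposure tables, the baseline for TEMAVs, laboratory shift tables and QTcF increments is unnamed or stated as Study Baseline in some places, while others point to Period 2 Baseline. It goes beyond missing detail, because protocol 9.7.1.8.5 and the general rule in SAP 6.2.1, applied literally, give these subjects a reference that precedes their placebo period.

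Under the Study Baseline wording, the affected subjects are 20% to 33% of each dose group, and a laboratory rate would be inflated by about 0.2 to 1.7 percentage points. This rests on 300 per arm, 0% to 50% placebo loss by Month 6, and an assumed 1% to 5% of former-placebo subjects with a persistent abnormality that arose on placebo. For QTcF no change in the expected rate is claimed, only that different subjects would be flagged. The plan should be corrected, since the tables are descriptive but central to the long-term safety account.

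**What to change.** State in SAP 6.2.1, and cross-refer from 3.6.4 and 3.6.6:

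- **Period 1 tables:** baseline is the last available value before the first randomized dose.
- **All 12-month LEM exposure tables, visit-based or not, including TEMAVs, shift tables and maximum QTcF increments:** baseline is the last available value before the subject's first lemborexant dose. That is Study Baseline for subjects on lemborexant from Period 1 and Period 2 Baseline for former-placebo subjects. Only values after that dose count as postbaseline.

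In 3.6.6, replace the unnamed baseline visit with this definition. In 3.6.4, name the baseline in the TEMAV rule and remove the leftover 12-month and 6-month upper-limit treatment groupings, which 3.6.1 does not define. Record the QTcF baseline as a clarification of protocol 9.7.1.8.5.

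The cost is SAP wording and one programming flag. No new data are needed.

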6.2.2 Handling of Missing Safety data, Drop-outs, and Outliers

For the purpose of summarizing maximum severity, if the severity of an AE is missing for a subject, then, if this subject has another AE with the same preferred term that has “severe” severity, the maximum severity of the AE will be noted as “severe”; otherwise the maximum severity will be noted as missing. Similarly, for the purpose of summarizing TEAE treatment relationship, if the relationship of an AE to study drug is missing, the AE will be noted to be related if there is another related AE with the same preferred term, otherwise this relationship will be noted as missing.

For determining treatment-emergent markedly abnormal laboratory values, a missing baseline laboratory value will be assumed to be of grade 0.

No special handling of missing data is planned for the analysis of any of the other safety variables.

Data exceptions or outliers will be determined by inspection of the tables, listings, and graphs in consultation with the clinical study team, if applicable.

All the listings will display the original missing values.

6.2.3 Visit Windowing

For the laboratory values, ECG, vital signs, weight, eC-SSRS, T-BWSQ, PGI-Insomnia, WPAI-GH and EQ-5D-3L, the following visit windowing rule in [Table 10](#) will be applied based on measurements from unscheduled visits and early termination visits to attain the measurement for analysis for the given scheduled visit.

Table 10 Windowing Rules for Safety Endpoints

Visit	Target Visit Day (in study days)	Visit Window (in study days)
Visit 4 (Month 1)	30	2 - 45
Visit 5 (Month 2)	60	46 - 75
Visit 6 (Month 3)	90	76 - 135
Visit 9 (Month 6)	180	136 – Prior to the date of first dose of Period 2 If subjects discontinue treatment, the visit window will be 136 – 187
Visit 12 (Month 9)	270	The date of first dose in Period 2 - 315 If subjects discontinue treatment, the visit window will be 188 – 315
Visit 15 (Month 12)	364	316 - 371
End of Study (EOS)	378	Nominal visit (ie., the visit captured in eCRF will be used)

In case of multiple assessments within the same visit window, the assessment closest to the target visit day will be used in data analyses; in the event of two assessments being equally close to the scheduled visit day, the latest assessment in time will be used.

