Subjects will be randomized, in a double-blind manner, to receive LEM5 or LEM10, or PBO (approximately 1:1:1, stratified by country and age group (<65 years old; ≥65 years old). Study drug will be dispensed and subjects will be provided with instructions to continue completing the Sleep Diary and taking study drug daily at home according to the same schedule and with the same restrictions as during the Run-In Period.

Period 1 will begin with the 1st dose of randomized study medication.

At the end of Month 6 (Period 2 Baseline), subjects who received PBO during Period 1 will undergo a 2nd randomization to receive either LEM5 or LEM10 (approximately 1:1, stratified by country and age group (<65 years old; ≥65 years old) during Period 2. Subjects who received lemborexant during Period 1 will continue to receive lemborexant at the same dose level during Period 2. Subjects will not be informed of the timing of the 2nd randomization (at the end of Month 6); allocation of dose will be double-blind. (revised per Amendment 04)

Subjects will continue to complete the Sleep Diary every morning throughout both Periods 1 and 2. They will return to the clinic at the end of Months 1, 2, 3, 6, 9, and 12. At each clinic visit, safety and tolerability will be assessed, including assessment of AEs, and a urine drug test will be carried out. At each clinic visit, except Month 12, the Sleep Diary will be reviewed for completeness, compliance will be checked, and study drug will be dispensed. At months 1, 3, 6, 9, and 12 the eC-SSRS will be administered. At the end of Months 1, 3, 6, 9, and 12, the ISI, FSS, the EQ-5D-3L and the PGI-Insomnia will be completed. At the end of Months 3, 6, 9 and 12, the WPAI-GH will also be completed. At predefined visits, a blood sample will be collected for PK analysis. (revised per Amendment 03)

At the end of Months 4, 5, 7, 8, 10, and 11, the site will telephone the subject to assess AEs, record concomitant medications, and review Sleep Diary entries. If any AE is clinically significant and requires follow-up, an Unscheduled Visit should be arranged as soon as possible. (revised per Amendment 03)

Period 2 will end with the completion of the 12-month visit. For analysis purposes, a subject who completes assessments through Period 2 will be considered to have completed the study.

Follow-up Period

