9.1.2.1 Treatment Period 1 (Period 1)

Period 1 will begin with the 1st dose of randomized study medication. During Period 1, subjects will complete sleep diaries daily in the morning, within 1 hour of waketime; sleep diaries will be checked on a monthly basis. The subjects will return to the clinic for the Month 1, 2, 3, and 6 visits. In between these clinic visits, at the end of Months 4 and 5, study

site personnel will conduct a phone call to the subject to review any issues with completion of the Sleep Diary and to query concomitant medications and AEs. (revised per Amendment 03)

At the Month 1 visit, standard safety assessments will be conducted, a blood sample will be collected for determination of plasma concentrations of lemborexant and its metabolites, the ISI, the FSS, the PGI-Insomnia, the EQ-5D-3L, and the eC-SSRS will be completed, unused study drug will be collected, study drug compliance will be assessed, and a new supply of study drug will be dispensed (Section 9.4.8). At the Month 2 visit, standard safety assessments will be conducted. At the Month 3 visit, assessments will be same as those at the Month 1 visit, . At the end of Month 6, all assessments conducted at the Month 3 visit will be repeated, and the WPAI-GH will also be completed. At completion of these assessments, Period 1 will end and Period 2 will begin. For analysis purposes, a subject who completes assessments up to Month 6 will be defined as a Period 1 completer. (revised per Amendment 03)

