10. At Baseline (Visit 3a): Reconfirmation of insomnia symptoms, as determined from responses on the Sleep Diary for the final 7 nights of the Run-in Period, such that sSOL ≥ 30 minutes on at least 3 of the 7 nights and/or sWASO ≥ 60 minutes on at least 3 of the 7 nights (revised per Amendment 03)
11. At Baseline (Visit 3a): Confirmation of regular bedtimes and waketimes such that the subject has a regular time spent in bed, either sleeping or trying to sleep, between 7 and 10 hours for the final 7 nights of the Run-In Period (revised per Amendment 03)
12. At Baseline (Visit 3a): Reconfirmation of regular bedtime, defined as the time the subject attempts to sleep, between 21:00 and 01:00 and regular waketime, defined as the time the subject gets out of bed for the day, between 05:00 and 10:00, for the final 7 nights of the Run-In period (revised per Amendment 03)
13. Willing and able to comply with all aspects of the protocol, including staying in bed for at least 7 hours each night (revised per Amendment 03)
14. Willing to not start a behavioral or other treatment program for insomnia during the subject's participation in the study

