6 DEFINITIONS AND CONVENTIONS FOR DATA HANDLING

6.1 Efficacy Data Handling

6.1.1 Baseline Efficacy

For the analyses of PBO-controlled endpoints (ie, Day 1 to Month 6), “Study Baseline” is defined as the data captured during the Run-In Period (or during the Baseline Period). For the analyses of data that are not placebo-controlled (ie, Month 7 to Month 12), data from the Month 6 visit will be used as the “Period 2 Baseline” for some analyses.

Unless otherwise specified, the Study Baseline measurement is the last observed measurement among all available measurements, including from unscheduled assessments, prior to the first dose of randomized study medication for a given assessment. For the following endpoints, baseline measurement is defined as follows:

- Sleep diary parameters: the mean of diary data entered on the last 7 mornings before Visit 3a during the Run-In Period
- ISI: Last available ISI measurement on or before Visit 3a (excluding Visit 1)
- FSS: Last available FSS measurement on or before Visit 3a (excluding Visit 1)
- EQ-5D-3L: Last available EQ-5D-3L measurement on or before Visit 3a (excluding Visit 1)
- WPAI-GH: Last available WPAI-GH measurement on or before Visit 3a (excluding Visit 1)

For each Sleep Diary parameter at baseline, if no more than 2 of the final 7 nights’ values are missing, the available values will be used to calculate the mean. If more than 2 values are missing, the parameter will be considered missing for baseline. For each Sleep Diary parameter during the treatment period and follow-up period, if at least 4 of the 7 nights’ values are available, the available values will be used to calculate the mean. If fewer than 4 values are available, the parameter will be considered missing for the corresponding time point.

For the analysis using the MMRM assuming MAR (no missing value imputation), the above handling will be used to obtain the average of weekly (7 days) diary parameter values.

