6.1.3 Visit Windowing

For the Sleep Diary, the following visit windowing rule in [Table 9](#) will be applied based on measurements from unscheduled visits and early termination visits to attain the measurement for analysis for the given scheduled visit.

Table 9 Windowing Rules for Efficacy Endpoints from Sleep Diary

Visit	Target Visit Day (in study days)	Visit Window (in study days)
First 7 nights	2	2 - 8
Visit 4 (Month 1)	30	24 - 30
Visit 5 (Month 2)	60	54 - 60
Visit 6 (Month 3)	90	84 - 90
Visit 7 (Month 4)	120	114 - 120
Visit 8 (Month 5)	150	144 - 150
Visit 9 (Month 6)	180	174 - 180 (or last 7 days prior to subject entering Period 2, whichever is earlier) *

Table 9 Windowing Rules for Efficacy Endpoints from Sleep Diary

Visit	Target Visit Day (in study days)	Visit Window (in study days)
Visit 10 (Month 7)	210	204 - 210
Visit 11 (Month 8)	240	234 - 240
Visit 12 (Month 9)	270	264 - 270
Visit 13 (Month 10)	300	294 - 300
Visit 14 (Month 11)	330	324 - 330
Visit 15 (Month 12)	364	Last 7 days from study days 358 - 371 (or last dose date + 1 for subjects who completed 12 months treatment, whichever is earlier)

*: If subjects discontinued the study and did not enter Treatment Period 2, last 7 days from study days 168 -180 will be used.

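### Where SAP Table 10 sets the analysis visit, a Month 6 assessment dated the same day as the first Period 2 dose goes to Month 9; the period TEAE rules also leave first-dose dates in no period

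*SAP*

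**What the plan says.** SAP Section 6.2.3, Table 10, gives windows for laboratory values, ECG, vital signs, weight, eC-SSRS, T-BWSQ, PGI-Insomnia, WPAI-GH and EQ-5D-3L. For subjects who enter Period 2:

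- Month 6 (target Day 180) runs from Day 136 to "Prior to the date of first dose of Period 2".
- Month 9 (target Day 270) runs from "The date of first dose in Period 2" to Day 315.

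Subjects who discontinue treatment have fixed windows instead (136–187 and 188–315). When several assessments fall in one window, the one nearest the target day is used. Only the End of Study row uses the nominal visit.

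SAP Section 6.2.1 takes the Period 2 safety baseline from the other side of the dose: "defined as the last non-missing measurement occurring prior to the first dose of the study medication in Period 2".

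The protocol sets the order of events. Section 9.1.2.1 says of the Month 6 visit: "At completion of these assessments, Period 1 will end and Period 2 will begin". The Synopsis says that at clinic visits other than Month 12 "compliance will be checked, and study drug will be dispensed", and Protocol Table 3 marks randomization and dispensing at Visit 9. Section 9.4.5 has drug taken at home immediately before sleep.

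SAP Section 3.6.3 defines a Period 1 TEAE as one emerging after the date of the first Period 1 dose and, at the latest, before the date of the first Period 2 dose. A Period 2 TEAE emerges after the date of the first Period 2 dose. A Run-In TEAE emerges before the date of the first Period 1 dose.

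**The concern.** The Table 10 boundary is drawn by calendar date, while the sequence it divides (assessment, dispensing, bedtime dose) can take place within one date. The evening dose then moves that day's earlier clinic assessments into a post-baseline Month 9 window. The same pre-dose safety measurement is the Period 2 Baseline under Section 6.2.1, so one record would be both baseline and Month 9. Period 1 is handled differently: the Month 1 window in Table 10 starts on Day 2, which keeps the first-dose day out of the post-dose windows.

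Month 6 closes the only placebo-controlled period, and the first database lock analyses data through that visit (SAP Section 3). At stake are the Month 6 values in the EQ VAS MMRM and the PGI-Insomnia chi-square tests, both on observed data, and in the by-visit WPAI-GH summary. If Table 10 also governs scheduled visits for the other assessments, the Month 6 summaries of laboratory values, ECG, vital signs, weight and eC-SSRS are at stake too.

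The adverse event rules have a related defect that does not depend on Table 10. Strict limits on both sides of a first-dose date leave that date in no period.

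**Working it through.** There is no planned figure to reproduce. The check applies the rules as written.

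**Inputs.** Month 6 window: Day 136 to (D − 1), where D is the study day of the first Period 2 dose. Month 9 window: D to Day 315. Month 6 visit within ±7 days of schedule (Protocol Table 3, footnote d). With the SAP target of Day 180, test days are 180 − 7 = 173, 180, and 180 + 7 = 187.

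**Assignment of an assessment on visit day V.**

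| V | D | Window as written |
|---|---|---|
| 173 | 173 (same date) | Month 9 |
| 180 | 180 (same date) | Month 9 |
| 187 | 187 (same date) | Month 9 |
| 173 | 174 (next date) | Month 6 |
| 180 | 181 (next date) | Month 6 |
| 187 | 188 (next date) | Month 6 |

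The result turns only on whether V = D. A bedtime before midnight gives V = D if the first Period 2 dose is taken on the night of the visit. A bedtime after midnight gives D = V + 1.

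**What becomes of the moved value.** Its distance from the Month 9 target is 270 − 173 = 97, 270 − 180 = 90 or 270 − 187 = 83 days. A real Month 9 visit within ±7 days (Day 263 to 277) is 0 to 7 days away. The nearest-to-target rule therefore keeps the real Month 9 value. The Month 6 value appears in neither column, unless another measurement between Day 136 and D − 1 fills Month 6. If there is no later measurement in the Month 9 window, the pre-dose value stands as Month 9.

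**Which assessments the window governs.**

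- EQ-5D-3L: SAP Section 3.7.1 says that the Section 6.2.3 window determines the analysis visit.
- PGI-Insomnia and WPAI-GH: Sections 3.7.2 and 3.7.2.1 say the same but cite 8.2.3 and 8.2.4, which this SAP does not contain. The intention is clear; the references are broken.
- Laboratory values, ECG, vital signs, weight and eC-SSRS: unclear. The lead-in to Table 10 names unscheduled and early termination measurements, and Section 3.6.4 summarizes laboratory data at scheduled visits. Against that, End of Study is the only row marked as nominal.
- T-BWSQ is given only at End of Study and is not touched.

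**Adverse events.** Let D1 and D2 be the dates of the first Period 1 and Period 2 doses. Run-In requires onset before D1, Period 1 requires onset after D1 and before D2, and Period 2 requires onset after D2. Onset on D1 or on D2 satisfies none of the three. Such an event can still meet the overall TEAE definition and is listed.

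**The case against.** The strongest reply is that Table 10 only lets off-schedule measurements stand in for a scheduled visit. Its lead-in can be read that way, and scheduled visits would then keep their nominal label. On that reading, only an unscheduled measurement on the boundary date is misplaced. Programming derivations are in separate documents (SAP Section 7) and may settle the matter. This stands for laboratory values, ECG, vital signs, weight and eC-SSRS, where the text does not decide the scope. It does not answer the direct statement for EQ-5D-3L or the parallel ones for PGI-Insomnia and WPAI-GH.

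Several stronger readings are tempting, and the documents do not support them:

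- **That Table 9 shows Table 10 to be out of line.** Its Month 6 row uses days 174–180, "or last 7 days prior to subject entering Period 2, whichever is earlier". That also ends before Period 2 entry, so there is no contradiction.
- **That former placebo subjects lose their Period 2 Baseline.** The safety baseline does not depend on Table 10. For EQ-5D-3L and WPAI-GH, Section 6.1.1 says "data from the Month 6 visit will be used as the" Period 2 Baseline, and the ordinary meaning is the visit rather than the window.
- **That the bedtime range gives the share affected.** The criterion asks for "regular bedtime, defined as the time the subject attempts to sleep, between 21:00 and 01:00". This is an eligibility rule for the run-in nights and says nothing about when first Period 2 doses were taken.
- **That all Month 6 safety output is at risk.** Markedly abnormal laboratory values and maximum ECG values are tabulated by period, not by a Month 6 column. Treatment discontinuers have fixed windows.

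**Conclusion.** The point holds as a minor one. As written, Table 10 moves a pre-dose Month 6 assessment to Month 9 when it shares a date with the first Period 2 dose, wherever the window sets the analysis visit. That is stated for EQ-5D-3L and intended for PGI-Insomnia and WPAI-GH. For the other Table 10 assessments made at Visit 9 it is conditional on the scope of the table.

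The size cannot be given. The documents do not report how many first Period 2 doses fall on the visit date; the share could be anything from none to all of those entering Period 2, so no number of lost records is claimed. A reader might infer that Month 6 data are in fact lost. The text permits that but does not show it.

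The effect is confined to observed-data exploratory tests and descriptive summaries. Primary and key secondary endpoints use Table 9 and are unaffected. The boundary is the same in every arm, so no between-arm bias is claimed.

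The adverse event gap follows from SAP Section 3.6.3 alone, whatever the scope of Table 10. It affects the attribution of events to a period, not whether they are recorded.

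**What to change.** 1. In Table 10, assign assessments on the date of the first Period 2 dose to Month 6 if made at Visit 9 or before the dose, and to Month 9 if made after the dose. Every assessment on that date then has a window, and all six cases in the table above fall in Month 6.
2. State whether Table 10 applies to scheduled visits or only to unscheduled and early termination measurements.
3. Correct the references to 8.2.3 and 8.2.4 in SAP Sections 3.7.2 and 3.7.2.1.
4. In SAP Section 3.6.3, assign an adverse event to a treatment period if it starts on or after that period's first-dose date, using onset time where it is recorded.

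The cost is a few lines of text and no new data. The downside of item 4 is that, without an onset time, some events that began before the dose on that day will count in the new period.
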